2.4 RISK/BENEFIT ASSESSMENT

2.4.1 Known Potential Risks

Liver biopsy is an invasive technique, with a well-described risk profile, and will be performed as clinically indicated and per the standards of the medical procedure. The biopsy procedure will be performed on the patients who have already been enrolled in other studies and required liver

image-guided biopsies, and we anticipate less than 5 minutes of added procedural time per participant using our designed biopsy device. We will exclude the patients who are not eligible for a routine image-guided biopsy, to minimize the adverse events. In case of any reactions, or detection of any potential risks to the participants or any predicted or un-predicted adverse events, the principal investigator will stop the procedure and all the adverse events will be reported in 24 hours. All the collected samples and data will be coded to maximize the participant's privacy. The records will be kept in locked drawers or password-protected electronic devices to ensure the safety of participants.

2.4.2 Known Potential Benefits

Patients with focal hepatic lesions need biopsies for accurate diagnosis, and the ones with small focal hepatic lesions approximately $l < 3$ cm required more accurate methods to guide the biopsy needle into the lesion. Accurate diagnosis of HCC or cancer is important in these patients since these patients are usually candidates for focal ablation and subsequent liver transplantation. Optical molecular imaging has been reported as a promising method for better detection of the tumors. Our null hypothesis is that there is discordance greater than 20% between the fluorescence signal during biopsy and histopathology. We anticipate that with the combination of both optical molecular imaging guidance and electromagnetic guidance, we can address issues of tumor heterogeneity, by guiding intra-tumoral sampling towards the most viable and aggressive lesion components to improve the biopsy yield.

2.4.3 Assessment of Potential Risks and Benefits

Since the selected participants are referred from other NIH research protocols that require an image-guided biopsy, they will be assessed for any risk of a percutaneous biopsy under anesthesia or conscious sedation per standard clinical care. Individuals eligible for biopsy based on standard clinical criteria and who have no contraindications to receiving ICG will be referred to this study and enrolled.

Participants will not be offered biopsy for the sole purpose of participation in this trial. Participation in this trial will not significantly alter clinical care. The procedure in this study requires intravenous administration of the FDA-approved agent (ICG) 24 hours before the intervention, and the biopsy procedure will be performed with FDA-cleared devices used as biopsy guides, which help the routine clinically used needle to enter the small lesion in the liver. Therefore, we anticipate that the participants in this study would be at minimal risk for using these devices compared to the ones who undergo a routine image-guided biopsy.

3 OBJECTIVES AND ENDPOINTS

OBJECTIVES	ENDPOINTS	JUSTIFICATION FOR ENDPOINTS
Primary		
To evaluate the feasibility of using both the optical molecular imaging technique and EM	Malignancy determination will be based on TBR: $TBR \geq 2$ will produce a malignant diagnosis,	The primary endpoint is the concordance between histopathology

OBJECTIVES	ENDPOINTS	JUSTIFICATION FOR ENDPOINTS
tracking during standard liver biopsies.	and TBR<2 will produce a benign diagnosis.	
outcomes and Target to Background Ratio (TBR) in vivo and ex vivo with a handheld OMI and PIC. Concordance is defined as a TBR ≥ 2. TBR will be calculated by dividing the mean fluorescence intensity within the lesion by the mean fluorescence intensity within the adjacent liver parenchyma.
 
This endpoint was chosen because fluorescence microscopy similarly shows a sharp delineation between malignant and normal tissue, with increased ICG uptake in malignant cells in preclinical models. This additive marker aids in better diagnostic procedures to diagnose liver cancer.

Secondary		
To assess the concordance of ICG fluorescence signal at the in vivo site of biopsy with the presence or absence of malignancy, as defined by pathology.	ICG fluorescent signal at the in-vivo site of biopsy using a combination of OMI and EM tracking	We are assessing concordance with the histopathology and measured TBR from two different environments with

OBJECTIVES	ENDPOINTS	JUSTIFICATION FOR ENDPOINTS
To assess the concordance of ICG fluorescence signal ex vivo (outside of body with camera) of biopsy with the presence or absence of malignancy, as defined by pathology.	ICG fluorescent signal ex vivo of the specimen obtained using a combination of OMI and EM tracking.	approved devices. We expect that they will match but we will need to confirm.

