1 PROTOCOL SUMMARY

1.1 SYNOPSIS

Title:	A Feasibility Study to Evaluate the Combination of Electromagnetic Tracking and Optical Imaging with Indocyanine Green (ICG) for Hepatic Biopsies
Study Description:	This is a pilot study to evaluate the feasibility of the combination of optical molecular imaging (OMI) and electromagnetic (EM) tracking for use during biopsy of intrahepatic lesions to assess the concordance between fluorescence ICG and histopathology for the diagnosis of liver cancer.
Objectives:	
Primary Objective:
 
 • To evaluate the feasibility of using both optical molecular imaging technique and electromagnetic tracking during standard liver biopsy. 
Secondary Objectives:
 
 1. To assess concordance of ICG fluorescence signal at the in vivo site of biopsy with the presence or absence of malignancy, as defined by pathology 2. To assess, in biopsy tissue, the concordance of ICG fluorescence signal ex vivo (outside of the body with camera) with the presence or absence of malignancy as defined by pathology
Endpoints:	
Primary Endpoint:
 
 • The determination of ICG fluorescent signal at the in-vivo site of biopsy using combination OMI and EM tracking will be based on Target-to-Background (TBR) such that TBR of ≥ 2 will produce a malignant diagnosis and TBR will produce a benign diagnosis. 
Secondary Endpoints:
 
 1. To evaluate the agreement between histopathology and ICG fluorescent signal in-vivo biopsy site using combined OMI and EM tracking using histopathology results as the gold standard. 2. To evaluate the agreement between histopathology and ICG fluorescent signal of the specimen ex-vivo using a combination of OMI and EM tracking.
Study Population:	Patients ≥ 18 years of age whose imaging findings suggest liver cancer (hepatocellular carcinoma) or other metastatic liver malignancy for whom image-guided percutaneous biopsy is separately indicated or planned to be performed.
Phase:	Non-randomized, Open Label, prospective pilot study.
Description of Sites/Facilities	Recruitment and investigational procedures will take place at the NIH Clinical Research Center in the Department of Radiology, Special Procedures.

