2.3.5 Results of pilot clinical trial for hepatic lesion sampling with optical guidance

Partners at MGH recently conducted the first-in-man trial of clinical liver biopsies using percutaneous OMI following injection of ICG ([Figure 7](#)). They recruited 6 patients for this pilot study [1]. The median size of the targeted lesions was 16 mm (range, 10–21 mm). Four of five biopsies (80%) yielded a positive pathologic diagnosis, and one biopsy specimen showed benign liver parenchyma.

[figure not shown]

Figure 7. Focal hepatic lesions on, A, MR image and, B, US image. C, 18F FDG PET scan shows avid lesions suspected of being malignancy. Intraprocedural optical molecular images confirmed the accuracy of the biopsy needle placement, by measuring increased fluorescence, E, in the target lesion relative to, D, normal liver. Optical images of the core biopsy specimen show visualized area of, F, focally increased ICG localization, G, in the core specimen. Final pathologic analysis of the core specimens revealed a granulomatous process.

[figure not shown]

Figure 8. Plot of normalized ICG

days following the procedures. We have shown that ICG imaging using these systems is a robust

Intraprocedural imaging of ICG fluorescence intensity at the tip of a standard introducer needle and within core biopsy specimens was feasible and added less than 5 minutes of procedure time in all patients. ICG was found to localize with TBRs greater than 2.0 (range, 2.4–13.4; median, 7.9) in all target lesions including primary HCC, metastatic CRC, and a non-neoplastic granulomatous process (Figure 8).

The difference between ICG fluorescence intensity between normal liver and focal hepatic lesions across the study cohort approached significance ($P = .06$). No trial-specific adverse events were observed up to 7

adjunct to conventional image guidance for patients undergoing biopsy of primary HCC, hepatic CRC metastasis, and non-neoplastic inflammatory processes, as well as thermal ablations.

[figure not shown]

Figure 9. NIH Clinical Center setup for an ultrasound/computed tomography –guided biopsy procedure with electromagnetic tracking guidance. FG: electromagnetic filed generator, NS: navigation.

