4 STUDY DESIGN

4.1 OVERALL DESIGN

This is a non-randomized, open-label prospective pilot study to evaluate the feasibility of the combination of optical molecular imaging (OMI) and EM tracking to guide liver biopsies and to detect and measure fluorescent ICG during intrahepatic biopsies. The primary endpoint is the concordance between the histopathology and measured ICG signal (typically TBR by handheld OMI for HCC). Concordance will be evaluated by confirming that all 4 of the following exist:

1. Diagnostic tissue specimen is obtained for conventional pathology analysis, defined by pathologist report of diagnostic liver lesion tissue
2. Imaging confirms that biopsy was taken from region desired
3. An ICG optical signal is obtained by ICG apparatus
4. EM tracking fusion image displays a location of biopsy.

Based on our preliminary data a TBR cut off value of 2.0 is typically considered positive for presence of malignant pathology. We expect that fluorescence intensity measurements will be able to accurately differentiate between benign and malignant lesions. This initial study will enroll 77 participants who have focal hepatic lesions suspicious for HCC or other metastatic liver disease, and for whom based on their primary research protocol, are directed to have a percutaneous diagnostic and or research biopsy.

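### Section 3 defines the primary concordance endpoint without pathology, sections 4.1 and 9.4.3 judge it by a technical checklist, and the plan leaves open whether agreement is primary and which kappa is tested

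*Combined protocol and SAP*

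**What the plan says.** **Definition of concordance.** The justification text in section 3 makes concordance between histopathology and TBR, in vivo and ex vivo, the primary endpoint, and continues: "Concordance is defined as a TBR ≥ 2". The Endpoints cell of the same row is a classification rule: TBR of 2 or more is a malignant call, "and TBR<2 will produce a benign diagnosis". Section 9 repeats that rule for both optical readings, takes histopathology as the gold standard and chooses Cohen's kappa. Section 9.1 describes concordance as the proportion of optical and histopathology results that match. Section 2.4.2 also compares signal with pathology; its null is "discordance greater than 20% between the fluorescence signal during biopsy and histopathology".

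**Checklist.** Sections 4.1 and 9.4.3 both say: "Concordance will be evaluated by confirming that all 4 of the following exist". The items are a diagnostic tissue specimen, imaging confirmation of the biopsy site, an optical signal obtained, and a tracked biopsy location displayed.

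**Status.** Section 4.1 says: "The primary endpoint is the concordance between the histopathology and measured ICG signal". The synopsis lists among its secondary endpoints: "To evaluate the agreement between histopathology and ICG fluorescent signal in-vivo biopsy site using combined OMI and EM tracking". Section 3's secondary rows include: "To assess the concordance of ICG fluorescence signal at the in vivo site of biopsy". Section 9.4.2, headed as the primary analysis, gives only timing. Section 9.4.3, headed as the secondary analysis, gives the checklist.

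**Test.** Section 9 plans two comparisons with histopathology, in vivo and ex vivo. Sections 9.1 and 9.2 state one pair of kappa hypotheses and one sample size, 77, without saying which comparison they concern.

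**The concern.** A concordance measure has to use both results. The section 3 sentence uses only one, so it scores a false positive as concordant and a correctly read benign lesion as discordant. The first case is realistic: in the pilot described in section 2.3.5, TBR exceeded 2.0 "in all target lesions including primary HCC, metastatic CRC, and a non-neoplastic granulomatous process". The checklist has the same gap in another form, because all four items can be met whether the optical call is right or wrong.

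What is at stake is whether the primary endpoint can be analysed and reported unambiguously. Three texts describe concordance differently, no passage says which prevails, and the section that should describe the primary analysis does not. Because agreement has no fixed status and the test no named comparison, the stated 5% error and 80% power are not attached to a particular result.

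**Working it through.** **Inputs.** Sections 9.1 and 9.2: prevalence of malignancy 80%; null kappa 0.4 with sensitivity 86% and specificity 55%; alternative kappa 0.7 with sensitivity 93% and specificity 80%; one-sided alpha 0.05; power 80%; N=77.

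**Step 1: reproduce the plan's N for one kappa.** With both raters 80% positive, the large-sample variance term is Q(k) = (1−k)[(1−k)(1−2k) + k(2−k)/(2×0.8×0.2)].
- Q(0.4) = 0.6 × [0.12 + 2.00] = 1.272
- Q(0.7) = 0.3 × [−0.12 + 2.844] = 0.817
- n = [(1.645√1.272 + 0.842√0.817)/0.3]² = 76.03, rounded up to 77
- Power at 77 = Φ[(0.3√77 − 1.645√1.272)/√0.817] = 80.5%

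The plan's figure is right, and it covers one comparison.

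**Step 2: literal section 3 rule against the true match.** Literal rule: q = P(TBR ≥ 2) = 0.8×sens + 0.2×(1−spec). True match: m = 0.8×sens + 0.2×spec. Chance agreement: pe = 0.8q + 0.2(1−q). Kappa = (m−pe)/(1−pe).

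| Scenario | Literal rule q (of 77) | True match m (of 77) | Kappa |
|---|---|---|---|
| Null pair, 86%/55% | 0.688+0.090 = 77.8% (59.9) | 0.688+0.110 = 79.8% (61.4) | 0.394 |
| Alternative pair, 93%/80% | 0.744+0.040 = 78.4% (60.4) | 0.744+0.160 = 90.4% (69.6) | 0.709 |
| Always positive | 100% | 80% | 0 |
| Perfect device | 80% | 100% | 1 |

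The match column recovers the 80% and 90% concordance of section 9.1, which confirms that the statistical section was built on matching. The literal rule moves by 0.6 percentage points between null and alternative, and ranks an always-positive device above a perfect one.

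**Step 3: the checklist.** A device wrong in every patient has m = 0, q = 0.2, pe = 0.8×0.2 + 0.2×0.8 = 0.32 and kappa = −0.32/0.68 = −0.47. It could still meet all four items in 77 of 77. The items measure technical success or evaluability, not agreement.

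**Step 4: in vivo or ex vivo.** Three places point to in vivo: the synopsis primary endpoint (signal at the in vivo biopsy site), section 2.4.2 (signal during biopsy) and section 4.1 (handheld device). Two keep it open: section 3 names both readings as primary, and section 9 joins both comparisons in one main objective.

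For illustration only, suppose each kappa were tested at one-sided 0.05 in the same 77 patients, with an assumed correlation of 0 to 0.9 between the two statistics. If either success counted, the error would be 9.75% (1 − 0.95²) down to 6.8%. If both were required, power would be 65% (0.805²) up to 76%. The documents give neither a decision rule nor a correlation.

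**The case against.** The strongest reply is that the section 3 sentence controls nothing. The sentence just before it sets TBR against histopathology, sections 9 and 9.1 give a complete rule, and no analysis section applies TBR alone. Most of this stands: the sentence is probably a misplaced positivity threshold, and the percentages in Step 2 describe a reading that was very likely not intended. It does not dispose of the point. The sentence sits in the table that defines the primary endpoint, sections 4.1 and 9.4.3 use the checklist instead of section 9.1's definition, and section 9.4.2 does not refer to the kappa test.

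It can also be said that the plan signals in vivo as the tested comparison. It does lean that way, but no sentence assigns the test.

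A reader might go further than the documents allow:
- *Patients will be scored on TBR alone.* No analysis section says so.
- *Type I error is 9.75%, or power is 65%.* These need an either-counts or both-required rule that no passage proposes. Independence is also implausible, because both kappas share patients and the pathology reference.
- *Section 9.4.2 permits interim testing.* It describes mostly per-patient analysis during enrolment, with no interim test or stopping rule. It is only a reason to name the kappa soon.
- *The pilot gives a count of false positives.* Section 2.3.5 does not say how the granulomatous lesion relates to the four positive diagnoses or to the benign-parenchyma biopsy. It shows that a non-malignant lesion can exceed 2.0, not how often this happened among the biopsies.

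**Conclusion.** The section 3 sentence is wrong as written, and the checklist in sections 4.1 and 9.4.3 does not measure what it is said to evaluate. Both conflict with sections 9 and 9.1, which are sound. On the plan's own prevalence and accuracy pairs, the literal rule gives 77.8% against 78.4%, where the true match is 79.8% against 90.4%, so it cannot separate null from alternative. No assumption beyond the plan's figures is needed for that result.

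Separately, agreement is primary in section 3's justification text and in section 4.1, but secondary in the synopsis, in section 3's secondary rows and under the section 9.4.3 heading. The single test is unassigned between two kappas, with in vivo indicated but not stated. This is a specification fault in the primary endpoint, to be corrected before further analysis. It does not show that N=77 is miscalculated, does not call the hypotheses or the kappa statistic into question, and has no bearing on patient care.

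**What to change.** 1. **Section 3.** Replace the sentence with: *Concordant = TBR ≥ 2 with malignant pathology, or TBR < 2 with benign pathology.*
2. **Sections 4.1 and 9.4.3.** Relabel the four items as technical success, and say that item 3 means a readable measurement at any TBR. Report the proportion meeting all four with an exact 95% confidence interval as the descriptive feasibility estimate (for illustration, 70/77 = 90.9%, interval 82.2% to 96.3%). Reconcile or remove the two objective-response definitions in section 9.4.1. One of them, fluorescence microscopy, is not among the procedures in Table 1 or section 6.1.
3. **Section 9.4.2.** Refer to the kappa test of sections 9 to 9.2 and state its analysis set: either all patients with a TBR and a diagnostic pathology result, or only those meeting all four items. Report kappa in the other set as a sensitivity analysis, with the number of patients outside each.
4. **Status and tested kappa.** Give agreement one status in the synopsis, both parts of section 3, section 4.1 and the section 9.4 headings. Have the sponsor name, before further analysis, the kappa that carries the one-sided 0.05 test (the text leans to in vivo), and report the other descriptively.

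Optional: state in section 9.2 that the 80% power applies to 77 evaluable patients, because section 5.5 counts patients who become inevaluable before biopsy toward accrual. The Step 1 formula gives 78% power with 73 evaluable and 76% with 69 (losses of about 5% and 10%, assumed).

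Cost: a wording amendment and two sponsor decisions (analysis set and tested kappa). Planned N, hypotheses and statistic stay as they are, and no new data or procedures are needed.

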4 STUDY DESIGN

4.1 OVERALL DESIGN

This is a non-randomized, open-label prospective pilot study to evaluate the feasibility of the combination of optical molecular imaging (OMI) and EM tracking to guide liver biopsies and to detect and measure fluorescent ICG during intrahepatic biopsies. The primary endpoint is the concordance between the histopathology and measured ICG signal (typically TBR by handheld OMI for HCC). Concordance will be evaluated by confirming that all 4 of the following exist:

1. Diagnostic tissue specimen is obtained for conventional pathology analysis, defined by pathologist report of diagnostic liver lesion tissue
2. Imaging confirms that biopsy was taken from region desired
3. An ICG optical signal is obtained by ICG apparatus
4. EM tracking fusion image displays a location of biopsy.

Based on our preliminary data a TBR cut off value of 2.0 is typically considered positive for presence of malignant pathology. We expect that fluorescence intensity measurements will be able to accurately differentiate between benign and malignant lesions. This initial study will enroll 77 participants who have focal hepatic lesions suspicious for HCC or other metastatic liver disease, and for whom based on their primary research protocol, are directed to have a percutaneous diagnostic and or research biopsy.

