9.1 STATISTICAL HYPOTHESIS

In terms of concordance, i.e. the proportion of EM+optical imaging and histopathology test results that match, the null hypothesis is that concordance $\leq 80\%$, and that the expected concordance (or concordance worth detecting) is 90%. Based on a positivity prevalence of 80%, i.e. 80% true malignant and 20% true benign, an 80% concordance can produce a kappa value ranging from 0 to 0.55; and a 90% concordance can produce a kappa value ranging from 0.62 to 0.74. Based on these numbers, the null and alternative hypotheses for this study are set in terms of kappa as follows:

- $H_0: \text{kappa} \leq 0.4$
- $H_1: \text{kappa} > 0.4$

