9.2 SAMPLE SIZE DETERMINATION

Based on the null kappa value $k_0=0.4$, a kappa value $k_1=0.7$ worth detecting, alpha (Type I error) equal to 0.05, 80% power, and a prevalence (true positive rate) of 80%, the resulting sample size from a one-sided test is 77.

Generally, $\kappa=0.4$ is considered as fair/moderate agreement, and $\kappa=0.7$ as substantial agreement.¹ With an 80% true positive rate, $\kappa=0.4$ corresponds to an 86% sensitivity and 55% specificity, and $\kappa=0.7$ corresponds to a 93% sensitivity and 80% specificity

With data on 77 cases, it is worthwhile determining the optimal cut-off point for TBR to confirm whether $TBR=2$ is optimal. This can be done based on Youden's index in receiver operating characteristic (ROC) analysis.

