9.4 STATISTICAL ANALYSES

9.4.1 General Approach

All patients who enroll in the study and complete the biopsy procedure will be evaluable for an objective response. Response is defined as localization of the target lesion and lends information regarding the feasibility of using the optical imaging device and EM tracking tool to guide liver biopsies. Fluorescence microscopy showing a clear delineation between malignant and normal tissue is also an objective response.

The main intervention of the study is the ability to improve biopsy guidance. Please note that standard pathology results of the hepatic biopsies will be part of routine clinical care and will be the responsibility of the NIH primary team to review and to provide appropriate follow up and clinical management. The tracking and fluorescence results will not be shared with participants, as these results are unlikely to have direct effect clinically on patient care. In addition to routine histological analysis, additional analysis for specific molecular markers will be performed in the NCI Laboratory of Pathology, as clinically indicated. However, all study-specific results are bench studies and will not be used in patient care decision making, thus we do not anticipate obtaining any incidental findings since the intervention is technical in nature regarding the biopsy procedure itself.

The main intervention of the study is the ability to improve biopsy guidance. Please note that standard pathology results of the hepatic biopsies will be part of routine clinical care and will be the responsibility of the NIH primary team to review and to provide appropriate follow up and clinical management. The tracking and fluorescence results will not be shared with participants, as these results are unlikely to have direct effect clinically on patient care. In addition to routine histological analysis, additional analysis for specific molecular markers will be performed in the NCI Laboratory Pathology, as clinically indicated. However, all study-specific results are bench studies and will not be used in patient care decision making, thus we do not anticipate obtaining any incidental findings since the intervention is technical in nature regarding the biopsy procedure itself.

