9.4.3 Analysis of the Secondary Endpoints

Concordance will be evaluated by confirming that all 4 of the following exist:

1. Diagnostic tissue specimen is obtained for conventional pathology analysis, defined by pathologist report of diagnostic liver lesion tissue
2. Imaging confirms that biopsy was taken from region desired
3. An ICG optical signal is obtained by ICG apparatus
4. EM tracking fusion image displays a location of biopsy.

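### The primary objective is feasibility, but the only formal test is of agreement (kappa > 0.4), which cannot show how often OMI and EM tracking worked; the four-item check that could is labelled concordance and has no analysis

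*Combined protocol and SAP*

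**What the plan says.** The synopsis gives the primary objective as "To evaluate the feasibility of using both optical molecular imaging technique and electromagnetic tracking during standard liver biopsy". Section 4.1 then states: "The primary endpoint is the concordance between the histopathology and measured ICG signal". It continues: "Concordance will be evaluated by confirming that all 4 of the following exist". The four items are a pathologist's report of diagnostic lesion tissue, imaging confirmation of the biopsy site, acquisition of an ICG signal, and an EM fusion display of the biopsy location.

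Section 9.4.3 repeats the same list, but under the secondary endpoints; its third item reads "An ICG optical signal is obtained by ICG apparatus". Neither section says in what share of participants the four items must hold, or how that share is to be estimated.

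Section 9.1 uses the word differently. There, concordance is "the proportion of EM+optical imaging and histopathology test results that match", with a null of at most 80% and an expected value of 90%. It then says "the null and alternative hypotheses for this study are set in terms of kappa as follows": H0 kappa ≤ 0.4 against H1 kappa > 0.4. Section 9.2 sizes the study at 77 for kappa 0.4 against 0.7.

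Section 9.4.2, on the primary endpoints, deals only with timing and reporting. Section 9.4.1 makes everyone who completes the biopsy evaluable for objective response and says "Response is defined as localization of the target lesion and lends information regarding the feasibility", again with no threshold.

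**The concern.** Feasibility asks how often the two technologies can be made to work during a standard biopsy. Kappa asks whether the TBR call agrees with pathology once both exist. The plan attaches its hypothesis, alpha, power and sample size to the second question and gives the first no estimate, denominator or interval.

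Two consequences follow. A significant kappa could be reported under a feasibility objective although it carries no information on how many participants lacked a signal, an EM display or diagnostic tissue. Equally, a system that works in nearly everyone but agrees only modestly with pathology could be reported as not feasible. And because the plan does not say how a participant without a TBR or a diagnostic core enters kappa, the test result itself depends on a choice still open when the data are seen. Section 9.4.2 has analysis running alongside enrolment, so that choice could be made with results in view.

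**Working it through.** **1. What the four items measure.** Take a participant with TBR 5 and benign histology from an adequate core at the confirmed site, with the EM location displayed. All four items hold, so Sections 4.1 and 9.4.3 count concordance; under Section 9.1 the results do not match. The two definitions therefore give opposite answers for the same participant.

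**2. The plan's sample size reproduces.** Inputs from Section 9.2: k0 = 0.4, k1 = 0.7, prevalence p = 0.8, one-sided alpha 0.05, power 80%. With equal margins, the large-sample variance of kappa per pair is (1−k)[(1−k)(1−2k) + k(2−k)/(2p(1−p))].
- At 0.4: 0.6 × [0.12 + 0.64/0.32] = 1.272, SD 1.128.
- At 0.7: 0.3 × [−0.12 + 0.91/0.32] = 0.817, SD 0.904.
- n = [(1.645 × 1.128 + 0.842 × 0.904)/0.3]² = 76.03 unrounded, hence 77. The arithmetic is not in dispute.

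**3. The plan's kappa-0.7 scenario.** Section 9.2 gives sensitivity 93% and specificity 80%.
- Observed agreement: 0.8 × 0.93 + 0.2 × 0.80 = 0.904.
- TBR-positive share: 0.744 + 0.040 = 0.784.
- Chance agreement: 0.8 × 0.784 + 0.2 × 0.216 = 0.670.
- Kappa: (0.904 − 0.670)/(1 − 0.670) = 0.71.

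**4. Handling A: participants without a pair are dropped.** Chance of rejecting kappa ≤ 0.4, simulated, one-sided 0.05:

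| Complete pairs | Sample SE | Null SE |
|---|---|---|
| 77 (no failures) | 85% | 81–82% |
| 54 (30% fail) | 76–77% | 68–69% |
| 38 (about half fail) | 65% | 53% |

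With 38 usable pairs from 77 participants, success is 38/77 = 49% (exact 95% CI 38% to 61%), a figure kappa does not contain.

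**5. Handling B: no signal is scored as TBR < 2, so benign.** All 77 stay in. At 50% optical failure:
- Observed agreement: 0.5 × 0.904 + 0.5 × 0.2 = 0.552.
- TBR-positive share: 0.5 × 0.784 = 0.392.
- Chance agreement: 0.8 × 0.392 + 0.2 × 0.608 = 0.435.
- Kappa: (0.552 − 0.435)/(1 − 0.435) = 0.21.

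The chance of rejection (sample SE) is 44% at 10% failure, 1.5% at 30% and under 0.01% at 50%.

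**6. EM display.** Neither TBR nor pathology needs the EM display to have appeared. A participant who fails only item 4 can still contribute a complete pair, so one of the two technologies named in the objective can fail without affecting the test.

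**7. An illustrative lower-bound rule.** The 80% figure is borrowed from the agreement null in Section 9.1 and is an assumption here. Requiring an exact one-sided 95% lower bound above 80%:

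| Denominator | Successes needed | Pass chance at true 90% |
|---|---|---|
| 77 | 68 (bound 0.805) | 76% |
| 70 | 62 | 74% |

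At n = 77 the pass chance is 4% at a true 80% and 99.5% at a true 95%.

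**The case against.** The strongest reply is that the plan deliberately operationalises feasibility as agreement. Section 3 pairs the feasibility objective with a TBR-based endpoint, and Sections 9.1 and 9.2 give it a null, an alternative, alpha and a sample size. Kappa > 0.4 is not the only stated threshold either: Section 9.1 has the 80% concordance null, and Section 2.4.2 a null of more than 20% discordance. This stands in part. It would be wrong to say that the trial has no decision rule. But all these thresholds measure agreement, and none measures how often the system worked.

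A reader might also infer that a system failing in half of patients would be declared a success. The documents do not support that as a flat statement. They neither drop failed cases nor retain them; the result holds under handling A and reverses under handling B. Even under A it is a probability, and it assumes that the remaining pairs keep the planned sensitivity and specificity. Nor do the documents suggest so high a failure rate: Section 2.3.5 reports that optical imaging was feasible in all patients of a six-patient pilot, and Section 2.3.11 describes 15 years of EM and fusion use at the site. The 50% figure is a stress test.

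Two objections limit the remedy, and both stand. OMI and EM tracking are bystanders (Sections 2.1 and 2.3.11), so items 1 and 2 largely reflect the standard biopsy, and a single composite would charge its failures to the new technologies. And participants who become ineligible before biopsy count toward accrual (Section 5.5), so the denominator may fall below 77. Finally, a pilot need not have a pass mark; an estimate with an interval can be enough.

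**Conclusion.** The concern holds in this form: the plan's only formal test cannot answer its primary objective; concordance has two incompatible definitions; the four-item list sits under the primary endpoint in one section and the secondary endpoints in another; and no rule covers failed measurements. Reading the four items as a technical-success measure is an interpretation, since the plan does not call them that, but it follows from their content.

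The missing rule is not a detail. In the plan's kappa-0.7 scenario at 80% prevalence, with 50% failure, it moves the chance of a positive test from about 65% (53% with the null SE) to under 0.01%. Handling A covers optical or tissue failure; handling B covers an absent signal only. The absence of a pass mark is not in itself the error. The absence of any planned estimate of technical success is. The sample size of 77 is correct for its inputs.

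**What to change.** - In Sections 4.1, 9.4.2 and 9.4.3, rename the four-item check technical success, and keep concordance for matching TBR and pathology results.
- Report technical success as a per-participant proportion with an exact 95% CI among all who received ICG and started the biopsy, counting any missing item as failure. Show items 3 and 4 (optical signal, EM display) separately from items 1 and 2 (tissue, site).
- State how participants without a TBR or without diagnostic tissue enter kappa, with the alternative handling as a sensitivity analysis.
- State that a positive kappa alone does not support a feasibility claim.
- A pass mark is the sponsor's choice. If one is wanted, fix it before analysis as a lower-bound rule on the actual denominator, as in step 7 of the working.

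The cost is a wording change and a little more reporting. No participants or procedures are added, since each item comes from the pathology report, the imaging, the optical record or the EM display. The downside is that, with a pass mark, the feasibility claim can fail: under the illustrative 80% rule, a system with true 90% technical success would miss it about one time in four.
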